**Figure 4. Schematic of Study Design**

## 6 Study Population

### 6.1 Selection Criteria

The following pages outline the specific inclusion and exclusion criteria for the study. Before the study inclusion, a subject must meet all of the inclusion and exclusion criteria.

#### 6.1.1 Inclusion Criteria

All subjects are required to meet the following inclusion criteria in order to be considered eligible for participation in this study:

|                    |   |
|--------------------|---|
| Inclusion Criteria | 

1. Patients 18 years of age and older;

2. Patients requiring epidermal closure after bi lateral total or partial (unicompartmental) knee arthroplasty;

3. Patients willing to be evaluated at discharge, 2 weeks and 6 or 8 -weeks post op.

 |
|--------------------|---|

#### 6.1.2 Exclusion Criteria

Subjects will be excluded from participating in this study if they meet any of the following exclusion criteria prior to initiation of the Zip Surgical Skin Closure Device.

|                    |  |
|--------------------|--|
| Exclusion Criteria | 

1. Known bleeding disorders not caused by medication;

2. Known personal or family history of keloid formation or scar hypertrophy;

3. Known allergy or hypersensitivity to non-latex skin adhesives;

4. Atrophic skin deemed clinically prone to blistering;

5. Any skin disorder affecting wound healing;

6. Any other condition that in the opinion of the investigator would make a particular subject unsuitable for this study.

 |
|--------------------|--|

### 6.2 Withdrawal of Subjects

Subjects may withdraw from the study at any time, with or without reason and without prejudice to further treatment. In all cases of withdrawal, the reason(s) for withdrawal (if given) will be recorded upon study termination.

In addition, the investigator may withdraw the subject due to any of the following situations:

- adverse event;
- any other reason determined by the investigator to be in the best interest of the subject.

Subjects withdrawn due to an adverse event should be followed until the event has been resolved or is stable, if at all possible.

## 7 Written Informed Consent

Written Informed Consent must be obtained for all subjects who are potential study candidates before any study-specific tests or procedures are performed.

The medical records of patients who are scheduled in clinic may be screened to prior to consent to assess eligibility for the study. Patients who meet general entry criteria will be asked to sign the study-specific, Institutional Review Board (IRB)-approved Informed Consent form before any study-specific tests or procedures are performed.

If the patient fails to meet study eligibility criteria or the patient's eligibility changes prior to randomization, the patient will be considered a screen failure and their participation will not count toward enrollment for the study. A Screening/Enrollment Log will be maintained to document select information about candidates who fail to meet the entry criteria.

## 8 Study Procedures and Enrollment

### 8.1 Duration of Subject Participation

Subjects enrolled in the study will participate until the Zip device and staples are removed from the subject and then continue participation until the final follow-up point (between 6 and 8 weeks post op).

### 8.2 Enrollment

Subjects that meet the inclusion/exclusion criteria will be invited to participate in the study and sign the Institutional Review Board (IRB) or Ethics Committee (EC) approved informed consent form. All subjects must provide written informed consent before undergoing any study related activity.

Subjects that meet all the eligibility criteria will be enrolled in the study and will serve as their own control. Subjects will be randomized in a 1:1 ratio to receive both the Zip device treatment and the staples on each knee.

### 8.3 Visit Schedule

The following table outlines the required study assessments.

**Table 1. Study Event Schedule**

|  | Before Procedure | Uni/TKA Procedure-Zip device or staple control Placement | Discharge 0-3 days Post Procedure | 14 days (+/-1 week) post Procedure | 6-8 weeks** (+/-4 days) post Procedure |
|--|------------------|--|-----------------------------------|------------------------------------|--|
| Study Initiation:  | X                |  |                                   |                                    |  |
| Informed Consent   | X                |  |                                   |                                    |  |
| Demographics/ Medical History  | X                |  |                                   |                                    |  |
| Clinical Status evaluation/site evaluation prior to wound closure device placement | X                |  |                                   |                                    |  |
| Inclusion / Exclusion Criteria Assessment  | X                |  |                                   |                                    |  |
| Left/Right Knee Randomization to Zip device or staples                             | X                |  |                                   |                                    |  |

|   |   |   |    |   |   |
|---|---|---|----|---|---|
| Photographs Taken   |   |   | X* | X | X |
| Adverse Events/Complications  |   | X | X  | X | X |
| Physician Evaluations (Satisfaction)  |   |   | X  |   | X |
| Physical Therapist Evaluations (ROM)  | X |   |    | X | X |
| Patient Evaluations(Pain, Comfort, Satisfaction)  | X |   | X  | X | X |
| Cosmetic outcome (CVAS, WES)  |   |   |    | X | X |
| Study Exit Form -CRF  |   |   |    |   | X |
| *Optional   |   |   |    |   |   |
| **Final visit will take place between week 6 and week 8 post surgery depending on surgeons standard visit schedule. |   |   |    |   |   |

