**Figure 2. Adjusting Incision Closure Tension**

The device remains on the skin for the recommended 7-14 days. During this period, patients may shower (but not soak in a tub or pool) with the device on. The device is removed by lifting the edge of the device and gently peeling along the incision, taking care not to apply stress to the incision. If there is a risk of skin stripping, an adhesive removal agent may be used during removal.

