### 8.4.4 Wound Closure Procedure / Protocol

The Zip device placement will be carried out following a standard protocol as described in the Instructions for Use (IFU)

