#### 8.4.6 Data to be collected at follow up visits

While performing the **2 week** follow up visit, record the following information:

- Cosmetic Outcome (Surgeon Rating)
  - Wound Evaluation Scale (WES) – The surgeon will conduct a follow up evaluation of the wound using the WES assessment. The WES evaluates six clinical variables including incision edges, contour irregularity, width, edge inversion, inflammation and overall cosmesis.
- Any complications/adverse events
- Range of Motion Measurements
- High definition photos will be taken of the incision/scar areas.
- Closure Method Comfort (Subject Rating)
  - A 5 point Likert Scale ranging from *Very Comfortable* to *Very Uncomfortable*
- Pain (Subject Rating)
  - A 11 point Numerical Rating Scale rating pain from *No Pain (0)* to *Worst Pain Imaginable (10)* will be used to measure general post- operative pain and specific incisional pain

While performing the **final** follow up visit (between week 6 and week 8), record the following information:

- Range of Motion Measurements (Physical Therapist Ratings)
- Pain (Subject Rating)
  - A 11 point Numerical Rating Scale rating pain from *No Pain (0)* to *Worst Pain Imaginable (10)* will be used to measure general post- operative pain and specific incisional pain
- Cosmetic Outcome (Subject & Surgeon Ratings)
  - Scar Satisfaction - A 5 point Likert Scale ranging from *Very Satisfied* to *Very Dissatisfied*
  - Scar Assessment - A 10 point Visual Analog Scale rating scar cosmesis from *0=Best Expected Scar* to *10=Worst Scar*
  - Wound Evaluation Scale (WES) – The surgeon will conduct a follow up evaluation of the wound using the WES assessment. The WES evaluates six clinical variables including incision edges, contour irregularity, width, edge inversion, inflammation and overall cosmesis.
  - Cosmetic Visual Analogue Scale (CVAS) – High definition photos will be taken of the incision/scar area at the final follow-up visit. Photos will be collected and evaluated using a VAS Scar Score by an objective independent panel (not affiliated with the study site) of up to 5 plastic surgeons.

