#### 8.5 Follow-up

The subject should be queried before discharge regarding any discomfort experienced after Zip device and staple use. After removal of both the Zip device and staples the status of the wounds should be assessed. Any Adverse Events should be noted. These data will be captured on the Case Report Forms. High resolution digital photographs should be taken after closure device removal (day 14) and at final 6 or 8 week follow-up visit. A user survey will be provided and will be required to be filled out as part of the follow-up.

Scar / cosmetic appearance will be evaluated on a visual analogue scales (CVAS). Physician and patient satisfaction with the closure techniques and the scar appearances will be evaluated.

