### DEVICE REMOVAL

The device may remain on the patient for up to 14 days. Care should be used to not disrupt the incision during removal. To remove device, begin at one end of the incision and gently peel device along the length of the incision. Do not use excessive force or pull in a direction that is away from the incision. To aid in the removal of the device, medical adhesive remover may be used. Continuously wipe a soaked cotton ball or swab along the lifted edge of the device as it is gently pulled along the incision. Adhesive residue may be removed with soap and water.

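### Does a 2-week visit window of days 7 to 21 conflict with a 14-day limit on device wear?

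*Combined protocol and SAP*

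**What the plan says.** Section 8.3 introduces Table 1 with the words "The following table outlines the required study assessments". The column for the second post-operative visit is headed "14 days (+/-1 week) post Procedure". It carries photographs, adverse events, range of motion, patient evaluations and the cosmetic scales. The table has no row for removal of the closures.

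Three other places bear on how long the Zip device stays on:

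- Section 4.1: "The device remains on the skin for the recommended 7-14 days".
- The IFU, under Device Removal: "The device may remain on the patient for up to 14 days".
- Section 8.5: "High resolution digital photographs should be taken after closure device removal (day 14"), and also "After removal of both the Zip device and staples the status of the wounds should be assessed".

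Section 8.4.4 refers to the IFU for application of the device: "The Zip device placement will be carried out following a standard protocol as described in the Instructions for Use (IFU". Section 8.4.6 lists the 2-week data, including "Closure Method Comfort (Subject Rating" and pain, and names neither removal nor its date. Section 8.1 mentions removal of both closures without giving a day.

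**The concern.** Of the scheduled visits, only the 2-week visit overlaps the recommended wear period, so a reader naturally assumes that the closures come off there. The link in section 8.5 between removal, photographs and day 14 strengthens that impression, because Table 1 and section 8.4.6 put photographs at the same visit. On that reading, a visit on day 18 is within window while the device has been worn beyond the IFU maximum, and visit timing alone would not reveal it.

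If removal does not wait for the visit, it takes place at a contact the protocol does not describe, and the time from removal to the 2-week assessment varies between subjects. Pain and closure comfort are listed secondary endpoints collected at this visit, and comfort rated with the closure in place may differ from comfort recalled days later. Section 13.1 also grades the relatedness of adverse events partly on whether they subside once the device is removed, which makes the removal date useful.

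**Working it through.** The plan gives no figure to reproduce here. The check is day arithmetic followed by a comparison of the sections.

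**Visit windows (Table 1)**

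- Discharge: days 0 to 3.
- 2-week visit: 14 − 7 = day 7 to 14 + 7 = day 21, so 21 − 7 + 1 = 15 permitted days.
- Final visit: 6 × 7 − 4 = day 38 to 8 × 7 + 4 = day 60. The footnote to Table 1 places it between weeks 6 and 8, which is days 42 to 56.
- Overlap with wear days 7 to 14: the 2-week visit only, whichever final window is used.

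**Where the 15 days fall relative to day 14**

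- Days 7 to 13: 7 days before.
- Day 14: 1 day.
- Days 15 to 21: 7 days after.

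**What a visit on days 15 to 21 would allow**

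- Removal at the visit: 15 − 14 = 1 to 21 − 14 = 7 days past the IFU maximum.
- Removal on days 7 to 14: the assessment comes 15 − 14 = 1 to 21 − 7 = 14 days after removal.
- Removal on days 10 to 14, which section 4.5 reports as typical in commercial use: 1 to 21 − 10 = 11 days after removal.

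These are the extremes the wording permits. The documents give no distribution of visit days, so none of this is a proportion of patients.

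**Do the sections contradict each other?** The wear statements agree: 7 to 14 days in section 4.1, up to 14 days in the IFU, day 14 in section 8.5. Table 1's tolerance attaches to a visit at which assessments are made, and no available sentence makes removal wait for that visit. A site can therefore keep to the stated wear period and see the subject on days 15 to 21 without breaking any provision. Read literally, day 14 in section 8.5 does not fit post-removal photographs at a visit on days 7 to 13 either. That suggests a nominal label for the 2-week visit rather than a second, stricter rule.

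**Which analyses could be affected?**

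- Primary: CVAS from photographs at 6 to 8 weeks, compared within subject by a paired t test. Even if removal waited until day 21, at least 38 − 21 = 17 days would separate it from the final visit.
- WES: the synopsis sets this endpoint at 6 to 8 weeks, so the 2-week WES is not a listed endpoint.
- Pain and comfort: the secondary analyses under section 9.2.2 call for summaries by closure method and specify no test. Table 1 also marks its combined pain, comfort and satisfaction row at discharge and at 6 to 8 weeks. Section 8.4.5 collects pain by discharge and section 8.4.6 collects it at the final visit.
- Safety: section 9.2.3 accumulates events from closure to the final visit and tabulates them by closure method. The removal date does not enter.

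**The case for a change.** The best case for acting is that the text never says how removal relates to the visit, that a device wear limit is involved, and that a sentence and two date fields would cost almost nothing. All of that is true. Section 8.4.4 cites the IFU for placement only, and section 8.4.6 does not repeat the order in section 8.5, where assessment follows removal.

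Less of it stands when each piece is examined. Section 8.4.4 is about placement, so citing the IFU for placement is natural, and the wear period is stated separately in section 4.1. The order of assessment is already given in section 8.5 and need not be restated. Section 8.5 sends its data to the case report forms, which are not in the available text; they may already hold removal dates, and the study schematic (Figure 4) cannot be seen either. Relatedness is an investigator's judgement, made with access to the subject's records.

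Two reservations remain. Section 8.4.6 names closure comfort only at 2 weeks, so Table 1's combined row does not prove that comfort itself is rated at every marked visit. And the 14-day limit concerns the Zip device; no available passage gives one for staples, so equal time since removal in the two knees is an assumption.

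**Conclusion.** The observation is accurate, but it describes a gap in operational detail, not a conflict between rules. At the edges of the wording it permits wear 1 to 7 days past the IFU maximum, or 2-week assessments 1 to 14 days after removal; it requires neither, and nothing shows how often either would happen.

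For the statistics, the consequence is small. The primary 6-to-8-week comparison is not shown to be affected. Both knees of a subject share the visit day, so late or early visits do not favour one closure. If both closures come off on the same occasion, as section 8.5 seems to presuppose, time since removal is shared as well. If they came off on different days, the 2-week comfort and pain summaries would need to be read with that in mind, which an analyst can do from the subject records.

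How sections 4.1 and 8.5, Table 1 and the IFU are reconciled in site practice is a clinical matter for the sponsor and can be settled in site training. No change to the plan follows.

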## 8.4 Study Procedures

### 8.4.1 Pre-Procedure

Prior to the subject's scheduled procedure, obtain informed consent, a medical history, pain assessment, ROM and record the subject's demographic (age, race, sex and date of birth) and baseline information (height, weight). Patient's medical records may be screened prior to obtaining consent to assess eligibility for the study.

(Please reference Figure 4 – Schematic of Study Design)

### 8.4.2 Randomization – Wound Closure Device Placement

All subjects will be screened for inclusion/exclusion criteria by study site personnel.

Once the screening and consent process is completed, subjects will be randomized to receive the Zip device (Treatment Group) on either the right or left knee by opening one of the sealed envelopes containing a randomization card. The subject will receive the staples (Control Group) on the opposing knee. The subject is considered enrolled into the study upon randomization and the subject disposition will be accounted for in study reports.

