## 1 ZIPS Study- Trial Protocol Synopsis

|                                 |   |
|---------------------------------|---|
| Study Title                     | ZIPS Study - Zip Incision aPproximation vs. Staple
A prospective, randomized controlled post-market study to compare the use of the Zip® Surgical Skin Closure Device versus conventional staples for skin closure in subjects having undergone bilateral knee arthroplasty – Protocol No. 006  |
| Overall Objective               | The objective of this study is to evaluate the Zip Surgical Skin Closure device versus conventional steel staple placement when utilized for surgical wound closure after bi lateral unicompartmental (UNI) or bi lateral total knee replacement (TKA).   |
| Study Device                    | ZipLine Medical Inc., Zip Surgical Skin Closure Device  |
| Indication for Use              | The Zip Surgical Skin Closure Device is indicated for use during and after skin incision procedures to approximate skin and hold together the skin edges until healing can take place.  |
| Study Design                    | A prospective, non-blinded, randomized, within patient control study. A total of up to 25 subjects (targeted min. n=22) requiring bilateral knee arthroplasty (unicompartmental or total) will be enrolled. Each subject will serve as their own control, since one knee closure will be with staples, and the other knee closure with Zip device. The order of patients will be randomized to receive Zip device on one knee and steel staples on the opposing knee. |
| Number of Subjects              | A total of up to 25 patients (serving as their own control) will be enrolled. There is anticipated patient fall out (screen failures) post procedure due to surgeon not knowing which procedure is required (total or unicompartmental) until time of surgery.  |
| Number of Sites                 | ≤ 3   |
| Duration of Study               | Each enrolled subject will be followed until 6 to 8 weeks post-procedure.   |
| Primary Effectiveness Endpoints | Wound healing as judged by the CVAS (Cosmetic Visual Analogue Scale) wound healing scale – From photos taken between 6 to 8 weeks post op visit – to be judged by panel of Plastic Surgeon blinded to treatment assignments.   |

|                                   |  |
|-----------------------------------|--|

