**Figure 1. Zip Surgical Skin Closure Device**

[figure not shown]
The Zip Surgical Skin Closure Device is applied to clean, dry skin after deeper tension-relieving (i.e., dermal or subcutaneous) sutures have been applied.

The device adheres to the skin adjacent to an incision by use of pressure-sensitive skin adhesives. A combination of acrylic and hydrocolloid adhesives are used to provide a skin-friendly environment while providing the necessary tack to maintain skin adhesion during the recommended wear time of the device (7-14 days).

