#### 9.3 *Sample Size Justification*

Since this is a Bilateral Study, with CVAS scores (Scores: 0 – 10), a paired “t” significant test is the most appropriate test as there is only one variable changing with the patients, i.e., type of closure device. A paired “t” test has more statistical power as well, and is more appropriate since the results will be comparing the treatment and control in a paired fashion.

The targeted minimum sample size of n=22 subjects (paired observations) was determined assuming an average difference ( $\Delta$ ) > 1.0, an hypothesized standard deviation of ~1.5, with the Power of Test set at 90%. Alpha Error for the test of differences = 0.025.

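### The left/right allocation is opened before surgery in an unblinded study, so nothing conceals it during incision and deep closure: an avoidable opportunity for performance bias in the primary CVAS comparison

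*Combined protocol and SAP*

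**What the plan says.** **Timing.** Section 8.4.2 has: "Once the screening and consent process is completed, subjects will be randomized to receive the Zip device" on the right or left knee, "by opening one of the sealed envelopes containing a randomization card". In Table 1 the row "Left/Right Knee Randomization to Zip device or staples" is marked only in the column before the procedure, although there is a separate column for the procedure and device placement.

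**Blinding.** The synopsis describes "A prospective, non-blinded, randomized, within patient control study". The photographs for the primary endpoint are "to be judged by panel of Plastic Surgeon blinded to treatment assignments".

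**Order of closure.** Section 4.1 says the Zip device "is applied to clean, dry skin after deeper tension-relieving (i.e., dermal or subcutaneous) sutures have been applied". The sample IFU also places deep sutures before the device and leaves them to usual practice. Section 8.4.4 refers to the IFU for Zip placement and says nothing about the staple knee or the deep layers.

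**What is recorded.** Section 8.4.3 lists the treatment and control sides and the incision lengths. It does not list deep-suture technique, operator or the order of the knees.

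**Premise of the analysis.** Section 9.3 justifies the paired t test because "there is only one variable changing with the patients, i.e., type of closure device".

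**The concern.** The randomised treatment is the skin layer alone. The incision and the deep closure come before it in the operation but after the allocation has been opened, and both can plausibly affect the scar. An operating team that knows the side could, without intending to, treat the two knees differently. The IFU even supplies a device-specific reason: it asks, for best results, that the incision edges be no more than 5 mm apart, which could prompt closer approximation on the Zip knee.

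The primary endpoint is a within-patient difference in CVAS. Any handling difference that goes systematically with the allocated closure enters that difference in full and cannot be separated from the device effect. Randomising left and right does not remove it, because it follows the allocation and not the side. The blinded photo panel protects the rating of the scar; it cannot undo a physical difference made in theatre.

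**Working it through.** **1. Sequence of events, set side by side.**

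| Step | Source | Allocation already opened? |
|---|---|---|
| Screening and consent | 8.4.2 | No |
| Envelope opened | 8.4.2; Table 1, column before the procedure | This step |
| Incision, both knees | 8.4.3 (length recorded) | Yes |
| Deep sutures, both knees | 4.1; IFU (not recorded in 8.4.3) | Yes |
| Skin closure, Zip or staples | 4.1, 8.4.4 | Yes; this is the randomised treatment |
| Photo rating at 6 to 8 weeks | Synopsis | Concealed from the panel |

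No text between the second and fifth rows delays disclosure to the operating team.

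**2. Inputs for an illustration.** Minimum n = 22 pairs, SD about 1.5 and target difference 1.0 (section 9.3); one-sided alpha 0.025 (sections 9.2.2 and 9.3). Assumptions: the 1.5 is the SD of the paired differences, and the bias is a constant b CVAS points in favour of Zip. The documents give no value for b, so a range is used.

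**3. The plan's own figure.** The normal approximation is n = [SD × (z(0.975) + z(0.90)) / difference]² = [1.5 × (1.960 + 1.282) / 1.0]² = 23.6, so 24. The exact paired t calculation gives 26. The planned 22 is close to the first; at 22 pairs the power is 87.8% (normal) or 84.6% (exact t). The present point does not depend on this, and the fix leaves n unchanged.

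**4. Effect of a bias on the type I error.** With no true device effect, the paired t statistic has a noncentral t distribution with 21 degrees of freedom and noncentrality b × √22 / 1.5. The critical value is 2.080. For b = 0.2 the noncentrality is 0.2 × 4.690 / 1.5 = 0.625.

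| Assumed bias b (CVAS points) | Noncentrality | P(significant for Zip), n = 22 |
|---|---|---|
| −0.3 | −0.938 | 0.2% |
| −0.2 | −0.625 | 0.5% |
| 0 | 0 | 2.5% |
| 0.2 | 0.625 | 8.6% |
| 0.3 | 0.938 | 14.4% |
| 0.5 | 1.563 | 32.0% |

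At the maximum enrolment of 25 pairs, biases of 0.2, 0.3 and 0.5 give 9.3%, 15.9% and 35.9%. A larger sample does not dilute a bias of this kind.

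**5. The opposite direction.** A bias against Zip lowers the false-positive rate but also hides a real benefit. With a true effect of 1.0 and b = −0.2, the expected observed difference is 1.0 − 0.2 = 0.8, and the power at 22 pairs falls from 84.6% to 66.5%.

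**The case against.** **The surgeon's knowledge is inferred.** Section 8.4.2 does not say who opens the envelope or when the operator is told, and the study schematic (Figure 4) is not available in the text reviewed. This stands as a limit on certainty. The inference is still well supported: the study is unblinded and no available text withholds the side.

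**No differential handling is shown.** A reader might infer that the surgeon will treat the knees differently, or that no scar difference could ever be credited to the skin closure. The documents support neither. They show an opportunity that has not been controlled, and bias arises only if technique changes with the allocated closure.

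**There is some mitigation.** Incision length is recorded, so a difference on that route would be visible. The IFU points to the deep sutures normally used, which suggests usual practice, but it does not bind the staple knee and leaves no record.

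**The illustration rests on assumed values.** The bias sizes have no source in the documents, and the direction could be either way. The table shows what a bias of a given size would do; it does not show that early allocation produces one.

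**Later opening is a partial remedy.** If the knees are operated on in sequence, the second knee's incision and deep closure may still be done with the side known. This stands, and it is why recording the deep-layer technique belongs in the fix.

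**Conclusion.** The point holds as a design weakness. The allocation is opened before surgery, nothing conceals it during the steps that precede the randomised closure, and apart from incision length those steps leave no record from which a difference could be detected. The premise in section 9.3 that only the closure device changes is therefore unprotected for the sole primary endpoint.

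The size of any resulting bias is unknown. If it were 0.2 to 0.5 points towards Zip, against a target difference of 1.0, the nominal 2.5% error would be about 9% to 32%; in the other direction a benefit would be masked. These figures assume 22 pairs, an SD of differences of 1.5 and a constant bias. The conclusion also rests on the reasonable but unstated point that the operating team learns the side when the envelope is opened. The change is cheap relative to what it protects and should be made.

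**What to change.** 1. In section 8.4.2 and Table 1, move randomisation to the procedure column. Open the subject's next sequentially numbered envelope in theatre, after the deep layers are closed and immediately before skin closure. If the knees are done in sequence, open it when the first knee reaches skin closure, with the order of the knees recorded beforehand.
2. Amend the linked wording. Section 8.4.2 counts a subject as enrolled at randomisation; section 7 defines screen failure relative to randomisation; sections 5.1 and 8.4.3 exit subjects who have a total replacement on one side and a unicompartmental on the other. All need to match the later time point. Many such mixed cases could then be identified before allocation.
3. In section 8.4.3, add deep-layer technique and operator for each knee to the recorded procedure data, so that any difference is visible.

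**Cost.** Protocol and CRF wording; sample size, visits, endpoint and test are unchanged. The envelope has to be handled in theatre, and both knees must be prepared so that either can receive Zip, since the IFU calls for skin preparation at the application site before surgery. With sequential surgery the second knee remains only partly protected, and the report should say so.
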